6.1.4.3 Baseline Procedure

Diagnostic angiography and PCI will be performed in accordance with standard hospital routine. Procedural data will be collected only after informed consent has been obtained.

- Angiographic eligibility criteria

Once it has been determined that a patient meets the angiographic eligibility criteria and a 38 mm EluNIR stent has been implanted or an attempt was made to implant a 38 mm EluNIR stent (ie, stent has advanced beyond the guide catheter), the patient will be screened for general eligibility criteria.

6.1.4.4 Post-Procedure and Discharge

- Enrollment and study stent information

Subject information will include the following. Refer to Section 19.1 for definitions.

- Demographics (e.g., age, gender, height, weight)

- Risk factors (dyslipidemia, hypertension, family history of premature coronary disease, tobacco use, and diabetes)
- Cardiac history (previous MI, intervention history, and past angina status according to CCS and Braunwald classifications)
- Baseline (pre-procedure) angina status
- DAPT medications (pre-procedure)
- Concomitant cardiac medication by category
- Assurance that informed consent has been obtained correctly

Collection of pre-procedure laboratory assessments and ECG data (if were done; if missing can be obtained as soon as possible after enrollment).

Angiographic data:

- Target lesion location
- Non-target vessel treatment, if applicable
- Anticoagulation administration
- Procedural complications that occur after the long EluNIR stent was advanced beyond the guiding catheter.
- Per-protocol DAPT medications
- Adverse events that occur after the long EluNIR stent was advanced beyond the guiding catheter.

Subjects who undergo PCI with a long EluNIR stent but do not consent to be enrolled in the study will not be included in the study and their data will not be collected.

- Post-PCI 12 lead ECG
- Post-PCI angina status
- Post-PCI adverse events with related laboratory tests results and details of any subsequent repeat coronary angiography and results of such, if applicable
- Post-PCI per-protocol DAPT medications
- Post-PCI concomitant cardiac medication by category
- CK and CK-MB or Troponin (I or T). Two post-PCI measures are recommended, but if early discharge is contemplated, at least one post procedure measurement 6-10 hours post-PCI is mandatory with the results known before discharge. The need for further cardiac biomarker measurement will be determined by the biomarker level, as detailed below in [Table 2](#):

Table 2: Patient Status as Indicated by Biomarker Levels

Biomarker Level	Patient Status	Action
<ULN CK-MB or Troponin* <7X ULN and	Clinically stable**	The patient may be discharged without additional levels.
1-3x ULN CK-MB or Troponin* 7-20X ULN and	Clinically stable**	The patient may be discharged but a second level is required at 12-18 hours prior to discharge. If the patient had an elevated troponin level immediately prior to study PCI and post-PCI level is lower than the immediate pre-PCI level, a second level is not required.
≥3x ULN CK-MB or Troponin* >20 X ULN	Not clinically stable	The patient may not be discharged until serial CK-MB or Troponin levels are decreasing and the patient is stable. If the patient had an elevated troponin level immediately prior to study PCI and post-PCI level is lower than the immediate pre-PCI level, a second level is not required.

*using conventional or hs-troponin assays with 99th percentile cutoff of 14 ng/L to 70 ng/L

** clinically stable- no chest pain, no ECG changes, no hypotension and no overt bleeding

6.1.4.5 30 Days (± 7 days)

- Angina status
- Adverse events with related laboratory tests results, ECGs, details of any subsequent myocardial infarction, hospitalization, or repeat coronary angiography and results of such, if applicable
- Details of any subsequent coronary interventions (e.g., repeat PCI or CABG)
- Compliance to protocol-required DAPT medications
- Use and changes in chronic antiplatelet medication regimen. Data are collected for the duration of the trial
- Concomitant cardiac medication by category

6.1.4.6 6 months (± 30 Days) & 1 year (±30 Days) Follow-up (by phone)

- Angina status
- Adverse events with related laboratory tests results, ECGs, details of any subsequent myocardial infarction, hospitalization, or repeat coronary angiography and results of such, if applicable
- Details of any subsequent coronary interventions (e.g., repeat PCI or CABG)
- Compliance to protocol-required DAPT medications
- Use and changes in chronic antiplatelet medications. Data are collected for the duration of the trial
- Concomitant cardiac medication by category

6.1.4.7 Additional (Unscheduled) Follow-up Visits

Additional subject visits may occur as clinically warranted. The following information will be collected at such visits:

- Data regarding adverse events with related laboratory tests results, ECG, details of any subsequent myocardial infarction, hospitalization, or repeat coronary angiography and results of such, if applicable. For suspected ischemic events, CK and CK-MB or Troponin (I or T) must be measured and 12 lead ECG obtained.
- Details of any subsequent coronary interventions (e.g., repeat PCI or CABG)
- Use and changes in chronic antiplatelet medication regimen. Data are collected for the duration of the trial
- Concomitant cardiac medication by category

6.1.5 Equipment to Be Used for Assessing the Clinical Variables and Arrangements for Monitoring Maintenance and Calibration

The Angiographic Core Lab will perform a qualitative coronary analysis (Pie Medical CAAS Workstation v. 5.11.2 Software) assessment of all target lesions pre-procedure, post-procedure. In-segment and in-stent target lesion minimal lumen diameter (MLD) and diameter stenosis (DS) will be determined by the angiographic core lab. Morphological characteristics (calcification, tortuosity, bifurcation, presence of thrombus), TIMI flow and blush will be assessed at baseline. Complications (no reflow, slow reflow, abrupt closure, new or worsening thrombus, distal embolization, perforation and dissection by NHLBI criteria) will be assessed intra-procedurally and at the end of the baseline procedure.

The Angiographic Core Lab will carry out intra- and inter-observer variability testing in accordance with the Standard Operating Procedures (SOP) of the Cardiovascular Research Foundation.

6.1.6 Procedures for the Replacement of Subjects

Discontinued subjects will not be replaced. Patients who do not consent to be enrolled in the study will not count towards the sample size of approximately 50 subjects and will not be included in the FAS.

Patients who are consented but do not meet eligibility and are not in the FAS will be in the Safety Analysis Set which will also include all FAS patients. Safety Analysis Set patients will be followed until resolution of any adverse events related to study procedures.

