6.1.4.2 Pre-Procedure Laboratory Assessments

The following laboratory assessments are to be performed (having been done as part of routine clinical care) prior to the baseline procedure.

Within 30 days prior to procedure:

- Complete Blood Cell Count (CBC)
- Creatinine, BUN
- Lipid profile (total cholesterol, LDL, HDL, triglycerides)

Within 24 hours pre-procedure:

- Electrocardiogram (ECG)
- Creatine kinase (CK) and creatine kinase muscle-brain isoenzyme (CK-MB) (For subjects with ACS, enzyme levels need to be within 8 hours of the procedure or have already been shown to be decreasing.)
- Troponin (T or I) where CK-MB is not available

Note: If any of the baseline tests were not obtained prior to the PCI procedure they may be obtained (including baseline biomarkers) as soon as possible after enrollment.

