7.6 Procedures That Take into Account All the Data

The analysis of the primary endpoint will be performed using the following datasets, as appropriate:

- **Full Analysis Set (FAS):** All subjects who have been enrolled into the trial, regardless of whether they received the study stent or not. Subjects are included in the FAS once the stent has been advanced beyond the guide catheter. If the study stent is not advanced beyond the guiding catheter, the patient will be de-registered and will not be considered part of the full analysis set.
- **Per-Protocol (PP) Analysis Set:** All subjects in the Full Analysis Set (FAS) with no major protocol deviations will be included in the Per-Protocol Analysis Set. Major protocol deviations include, but are not limited to, enrollment of a subject:
 - ✓ whose informed consent was not properly obtained
 - ✓ who did not meet all of the inclusion or exclusion criteria
 - ✓ who did not receive at least 6 months of DAPT post baseline procedure
- **Safety Analysis Set:** The safety analysis set will include all subjects, including de-registered subjects, who signed an informed consent and who had any trial-related activities.

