Procedure success is defined as achievement of a final in-stent diameter stenosis of <30% (by QCA) using the assigned device and/or with any adjunctive devices, without the occurrence of cardiac death, Q wave or non-Q wave MI, or repeat revascularization of the target lesion during the hospital stay.

ADVERSE DEVICE EFFECTS

See Section 14 for definitions of adverse device effects (serious, anticipated, and unanticipated)

ADVERSE EVENTS

See Section 14 for definitions of adverse events (non-serious and serious)

ANALYSIS DATA SETS

Full Analysis Set (FAS)

If the study stent is not advanced beyond the guiding catheter, the patient will be de-registered and will not be considered part of the full analysis set. Patients not receiving the study stent after it has been advanced beyond the guiding catheter will be analyzed in the full analysis set. Patients enrolled in the trial with major deviations will also be analyzed in the full analysis set.

Per Protocol (PP Population)

Patients who receive the study stent with no major protocol deviations as detailed in Section 7.6 will be included in the Per Protocol Analysis Set.

Safety Analysis Set

The safety analysis set will include all subjects who signed an informed consent and have had any trial related activities including de-registered subjects.

ANGINA PECTORIS

CCS Classification of Stable Angina

- I. Ordinary physical activity does not cause angina, such as walking or climbing stairs. Angina occurs with strenuous or rapid or prolonged exertion at work or recreation.
- II. Slight limitation of ordinary activity. Angina occurs upon walking or climbing stairs rapidly, walking uphill, walking or stair climbing after meals, or in cold, or in wind, or under emotional stress, or only during the few hours after awakening. Angina occurs if walking more than two blocks on the level or climbing more than one flight of ordinary stairs at a normal pace and in normal conditions.

III. Marked limitation of ordinary activity. Angina occurs upon walking one or two blocks on the level or climbing one flight of stairs in normal conditions and at a normal pace.

IV. Inability to carry on any physical activity without discomfort. Angina syndrome may be present at rest.

Braunwald Classification of Unstable Angina

Severity		Clinical Circumstances		
		A	B	C

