3.0 ANALYSIS SETS

Full Analysis Set (FAS): All subjects who have been enrolled into the trial, regardless of whether they received the study stent or not will be included in the FAS. Subjects are included in the FAS once the EluNIR 38 mm stent has been advanced beyond the guide catheter. If the study stent is not advanced beyond the guiding catheter, the patient will not be enrolled in the trial.

Per-Protocol (PP) Population: All subjects in the Full Analysis Set (FAS) with no major protocol deviations as identified by the Medical Monitor will be included in the Per-Protocol Analysis Set. Major protocol deviations may include the following categories:

- Informed consent was not properly obtained
- Inclusion or exclusion criteria deviations
- Not receiving DAPT post-baseline procedure according to the standard of care

Major protocol deviations will be identified by the Medical Monitor prior to the database lock for the primary analysis.

Safety Analysis Set: All subjects, including subjects who are consented but do not meet eligibility criteria and not in the FAS will be included in the Safety Analysis Set. Safety Analysis Set will also include all FAS patients.

Table 2 summarizes the analysis sets to be used for each type of analyses.

 Cardiovascular Research Foundation	FORM		Document N° BIO-TMP-0702 Revision: 00
	TITLE SAP Template		Effective date: 16-Mar-2018 Department: BIO

Table 2 Analyses and analysis sets

Endpoint	FAS	PP Analysis Set	Safety Analysis Set
Primary endpoint	X	X	
Secondary endpoints	X	X	
AEs, Other Safety Data			X
Demographics/baseline characteristics	X		
Angiographic Core Lab Analysis	X		

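### A consented, treated subject judged ineligible is inside the Full Analysis Set under one part of the plan and can be outside it under another, and the judgement can follow the acute result

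*Protocol*

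**What the plan says.** Two descriptions of the analysis sets stand side by side.

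- **Outside the FAS.** Protocol 6.1.6: "Patients who are consented but do not meet eligibility and are not in the FAS will be in the Safety Analysis Set". SAP 3.0 has the same idea: "subjects who are consented but do not meet eligibility criteria and not in the FAS will be included in the Safety Analysis Set". On follow-up, Protocol 6.1.6 adds: "Safety Analysis Set patients will be followed until resolution of any adverse events related to study procedures".
- **Inside the FAS.** Protocol 7.6: "Subjects are included in the FAS once the stent has been advanced beyond the guide catheter". The same section lists as a major deviation the enrollment of a subject "who did not meet all of the inclusion or exclusion criteria", and major deviations remove a FAS subject from the per-protocol set. Protocol 19.1 confirms it: "Patients enrolled in the trial with major deviations will also be analyzed in the full analysis set". The only exit from the FAS that 7.6 and 19.1 name is a stent that never passed the guiding catheter.

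Protocol 6.3.4 defines enrollment as three things together: meeting all general and angiographic criteria, passage of the stent beyond the guiding catheter, and consent signed after the procedure.

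On timing, Protocol 6.1.4.3 says that once the stent has been implanted or attempted, "the patient will be screened for general eligibility criteria". Protocol 6.1.4.2 says of baseline tests not done before PCI that "they may be obtained (including baseline biomarkers) as soon as possible after enrollment". The primary endpoint is analysed in the FAS, with a per-protocol analysis alongside (Protocol 7.2.2).

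**The concern.** In a single-arm trial, the denominator of the primary proportion should be fixed by something that cannot depend on the result. Here it may not be. If ineligibility can place a consented, treated subject in the Safety Analysis Set only, and ineligibility is judged after the stent attempt, then the person judging may already know that the stent was not delivered or that it malfunctioned. Either event is a failure of the primary endpoint.

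An exclusion related to failure pushes the success rate up. It may also be hard to undo, because follow-up tied to the resolution of procedure-related adverse events need not reach day 30, so MACE status may never be collected. The SAP's missing-data analyses (4.4 and 5.2.2) impute for subjects who lack the endpoint within the analysed population. They do not bring back a subject who was placed outside the FAS.

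**Working it through.** **Which rule applies to one subject.** Take a subject whose 38 mm stent passed the guiding catheter, who signed consent, and who is then found to fail a general exclusion criterion.

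| Source | Result for this subject |
|---|---|
| Protocol 7.6 and 19.1 | In the FAS; out of per-protocol |
| Protocol 6.1.6, SAP 3.0 | May be outside the FAS; Safety set only |
| Protocol 6.3.4, read literally | Not enrolled, because not all criteria are met |

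SAP 3.0 holds both descriptions: it uses the stent-advancement trigger for the FAS and lists eligibility deviations among the per-protocol exclusions. The Medical Monitor's review before database lock decides per-protocol membership. Nobody is named as deciding FAS membership.

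**Who is in the group that 6.1.6 describes.** Consent comes after the procedure. Protocol 6.3.4 approaches only patients whose stent was advanced beyond the guiding catheter, and bars consent if the stent was not advanced into it. Apart from consent taken in error, or a stent that entered the guide without leaving it, a consented ineligible patient is therefore a treated patient.

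**Which criteria are judged late.** The general criteria are inclusions 1–5 of 8 and exclusions 1–27 of 32. The rest are angiographic and are judged on the immediate pre-procedure angiogram (Protocol 6.4.1). The late judgement therefore concerns general criteria, for example clinically significant liver disease, or the haemoglobin, platelet and eGFR limits when those tests were first drawn after PCI.

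**The plan's own figure.** Protocol 7.1 gives 80% probability of at least one device-related adverse event at 3.2% incidence with n = 50. Check: 1 − (1 − 0.032)^50 = 0.803. It reproduces. Even at n = 47 it is 1 − 0.968^47 = 0.783. Adverse events are in any case summarised in the Safety set, which keeps the moved subjects, so the sample-size statement is not at issue.

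**Effect on the primary proportion.** The documents give no expected success rate, so the counts are assumptions. With f true failures among 50 consented, treated subjects and k of those failures moved out of the FAS, the reported rate is (50 − f)/(50 − k). Intervals are exact (Clopper-Pearson) 95%, the method that the plan specifies.

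| f | k = 0 | k = 1 | k = 2 | k = 3 |
|---|---|---|---|---|
| 3 | 47/50 = 94.0% (83.5–98.7) | 47/49 = 95.9% (86.0–99.5) | 47/48 = 97.9% (88.9–99.9) | 47/47 = 100% (92.5–100) |
| 5 | 45/50 = 90.0% (78.2–96.7) | 45/49 = 91.8% (80.4–97.7) | 45/48 = 93.8% (82.8–98.7) | 45/47 = 95.7% (85.5–99.5) |
| 8 | 42/50 = 84.0% (70.9–92.8) | 42/49 = 85.7% (72.8–94.1) | 42/48 = 87.5% (74.8–95.3) | 42/47 = 89.4% (76.9–96.5) |

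Each moved failure adds about 2 points. Moving one success instead, with f = 5, gives 44/49 = 89.8%. The bias arises only if removal is related to the outcome.

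**The case against.** The strongest reply is that 6.1.6 does not order anyone out of the FAS. It speaks of patients who are ineligible and also not in the FAS, and gives that residual group a home. A reader might infer that the protocol directs removal of ineligible subjects; the wording does not go that far. Two reconciling readings are available.

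- *The group is those whose stent was not advanced.* Advancement is itself inclusion criterion 3, and 7.6 and 19.1 mention de-registered subjects in the Safety set. But 6.3.4 leaves almost nobody who is both consented and in that position.
- *Ineligibility found before enrollment means Safety set only; found after, FAS.* This fits the words, and it would keep subjects with late laboratory tests in the FAS, since those tests are described as following enrollment. But no section draws the line, 6.3.4 makes eligibility part of enrollment, and the pre-enrollment judgement is itself made after the stent attempt. This reading restates the problem.

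Other parts of the reply stand:

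- A reader might infer that every criterion is judged with the result in hand. Angiographic eligibility is not, and Protocol 6.3.1 says that all criteria refer to the condition before PCI.
- A reader might infer that the full primary outcome is known at screening. The site can see a failed delivery or a malfunction, but the endpoint also needs core-laboratory QCA and adjudicated 30-day MACE.
- Protocol 6.3.4 requires all eligible patients to be approached whatever the result, and a log of every 38 mm stent advanced beyond the guiding catheter, with eligibility and consent. Protocol 13.1 has records reviewed before the approach. SAP 5.1.1 tabulates numbers screened and enrolled and adherence to the criteria. Selective removal would leave a trace, and the group should be small.
- The trial is descriptive, with no performance goal, so no decision threshold can be crossed. The shifted estimates all lie within the interval around the unshifted one when f = 5.

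These safeguards reduce the risk. None of them settles FAS membership once a treated subject has consented.

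**Conclusion.** The point holds as an unresolved conflict over who is in the primary analysis set. The route to bias runs through the general criteria and through acute failures that are visible at the end of the procedure. Its size depends on assumed counts: about 2 points per failed case moved out, for example 90.0% to 91.8%, 93.8% or 95.7% for one to three cases under an assumed 45/50. Nothing in the documents suggests that anyone has used this latitude or intends to. The matter deserves correction before the data are seen because the affected quantity is the primary result, the group is small enough to handle fully, and lost 30-day follow-up may not be recoverable.

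**What to change.** State one rule in Protocol 6.1.6, 6.3.4, 7.6 and 19.1 and in SAP 3.0:

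1. Every consented subject in whom the 38 mm stent was advanced beyond the guiding catheter is in the FAS and has the full scheduled follow-up, whenever an eligibility failure is found. Eligibility failures leave the per-protocol set only. This is what 7.6 and 19.1 already imply.
2. Delete from 6.1.6 and SAP 3.0 the words that allow an ineligible consented subject to be outside the FAS. Limit the shorter follow-up in 6.1.6 to consented subjects whose stent did not pass the guiding catheter; as written it covers the whole Safety set, which includes the FAS.
3. Judge eligibility on the pre-PCI condition, as 6.3.1 says. Where a baseline test was first obtained after PCI, as 6.1.4.2 permits, flag it and do not use it to take a subject out of the FAS. Requiring pre-PCI records for every criterion would conflict with 6.1.4.2.
4. Report from the screening log how many patients were judged ineligible after stent advancement but before consent, with the reason and, where this can be reported without consent, the acute procedural result. The FAS rule does not reach these patients, and Protocol 6.1.4.4 bars collecting the data of patients who do not consent.

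The cost is wording in two documents, follow-up of probably a few more subjects, and a short screening-log table. The FAS becomes slightly more mixed and the primary rate may be a little less favourable. The planned per-protocol analysis still excludes subjects with eligibility failures.

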6.2 Study Device

6.2.1 Description of the Exposure to the Study Device

All subjects will have a single treatment with the (38 mm) EluNIR study stent which is approved and marketed in Israel.

6.2.2 List of Any Other Medical Devices or Medication to Be Used During the Clinical Investigation

The stent implantation will be part of a standard cardiac intervention which includes accessory medical devices such as arterial sheaths, guidewires, guiding catheters, inflation devices, and other accessories. Standard medications such as heparin, bivalirudin, contrast media, nitroglycerin, and relaxants are used. After the procedure, the subjects will receive DAPT for a minimum of 6 months, 12 months in ACS patients (see Section 6.4.8.3) as well as other medications as prescribed to control other co-morbidities such as hypertension, hypercholesterolemia, and heart failure. All of these accessory medical devices and medications are approved to be on the market.

